A Preliminary Study of Prophylactic Fentanyl Sublingual Spray (FSS) for Exercise-Induced Breakthrough Dyspnea

Principal investigator: [name]

Supportive Care Co-investigator: [name]

Collaborators: [name], [name]

Table of Contents

A. Study Objectives	2
B. Background.....	2
C. Experimental Approach	2
D. Statistical Analysis	12
E. Data Confidentiality Procedures.....	13
F. References.....	14

A. Study Objectives

Primary objective:

To determine the **effect of prophylactic fentanyl sublingual spray** (FSS, 15-25% and 35-45% proportional doses) on the **intensity of exercise-induced dyspnea** (modified Borg scale) between the first and second shuttle walk tests. *We aim to estimate the effect size for both FSS arms to inform a larger, adequately powered confirmatory randomized controlled trial.*

Secondary objectives

A.2. To determine the **effect of prophylactic FSS** (15-25% and 35-45% proportional doses) on **walk distance and adverse effects** between the first and second shuttle walk tests. *We hypothesize that FSS is superior to no FSS in increasing walk distance and has limited side effects in opioid tolerant individuals.*

A.3. To compare the **intensity of exercise-induced breakthrough dyspnea** between high (35-45% proportional dose) and low (15-25% proportional dose) doses of prophylactic FSS. *We hypothesize that higher doses of FSS is superior to lower doses FSS in reducing dyspnea at the end of the shuttle walk test.*

B. Background

Dyspnea is a subjective awareness of difficulty breathing, which may be associated with the distressing sensation of suffocation. It is one of the most common and most feared symptoms among cancer patients, occurring in up to 70% of patients in the last 6 weeks of life ^{1,2}. Dyspnea is associated with fatigue, anxiety, decreased function and quality of life, and increased mortality ^{3,4}.

In a study examining 70 patients with dyspnea, 43 (61%) reported breakthrough (episodic or incidental) dyspnea only, 13 (19%) had constant dyspnea only, and 14 (20%) experienced both constant and breakthrough dyspnea. A substantial proportion of the patients with breakthrough dyspnea (18/57, 32%) presented with 5 or more episodes per day, and the majority of episodes lasted <10 minutes ⁵. Breakthrough dyspnea is particularly challenging to treat because of its transient and episodic nature.

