Treatment options for breakthrough dyspnea. Although systemic opioids are established for management of dyspnea at rest, there are currently no definitive evidence-based options for breakthrough dyspnea. In a case series, Bruera et al. reported the use of rescue morphine given subcutaneously for 312 episodes of breakthrough dyspnea in 45 cancer patients. After 30 minutes, 90% reported no to mild dyspnea ⁸. Based on this study, most clinicians use a dose similar to the rescue opioid dose for breakthrough pain (i.e. 10-20% of total daily dose) to manage breakthrough dyspnea. However, a more recent double-blind randomized controlled trial comparing systemic hydromorphone (oral or subcutaneous (SC)), nebulized fentanyl, and nebulized saline for breakthrough dyspnea found no significant difference in dyspnea relief at 10 minutes between the treatment arms ¹². One of the reasons may be due to the short duration for the primary endpoint (10 minutes) and the fact that the investigators used mostly oral hydromorphone, which reaches peak concentration only 45-60 minutes later. We recently completed a preliminary study examining the role of subcutaneous fentanyl for breakthrough dyspnea, and found a significant improvement in both dyspnea scores and walk distance before and after the study ¹³. To date, the evidence for opioid use for breakthrough dyspnea in cancer patients remains limited (Table 1). A recent review on the role of opioids in breakthrough dyspnea supported a promising therapeutic effect in cancer and non-cancer settings ¹⁴. Further research is necessary to improve the management of this distressing and debilitating symptom.

Table 1. Studies of Opioids for Breakthrough Dyspnea in Cancer Patients

Study	Methodology and patients	Agent and dose	Outcome
Bruera et al. Ann Intern Med 1993 ⁸	Prospective case series (45 cancer pts)	SC morphine 312 doses given (same dose as pain breakthrough)	After 30 minutes, 90% reported no-mild dyspnea; 5% mod-severe dyspnea
Benitez-Rosario et al. JPSM 2005 ¹⁵	Retrospective case series (4 cancer pts)	OTFC 800mg/1200mcg 60mg/800mcg 120mg/600mcg 15mg/400mcg	RR decreased Dyspnea decreased by 90-100% in 20-60 minutes
Sitte et al. JPSM 2008 ¹⁶	Retrospective case series (1 cancer pt, 2 heart failure pts)	Intranasal fentanyl 1/6 of MEDD	RR decreased, improved O ₂ saturation in all 3 patients Dyspnea scores not reported

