Gauna et al. JPM 2008 ¹⁷	Prospective case series (2 COPD pts, 2 cancer pts) 10 episodes	OTFC 30mg/200mcg 720mg/400mcg 20mg/200mcg	RR decreased Dyspnea decreased by 90-100% in 20-60 minutes

24mg/200mcg			
Charles et al. JPSM 2008 ¹²	Prospective, double blind crossover RCT (20 cancer pts)	Systemic (mostly oral) hydromorphone Nebulized hydromorphone Nebulized saline	Dyspnea decreased similarly in all 3 arms (1.0, 0.9, 0.8)
Hui et al. JPSM 2014 ¹³	Prospective, double blind crossover RCT (20 cancer pts)	Subcutaneous fentanyl Nebulized hydromorphone Nebulized saline	Dyspnea and walk distance significantly improved in the fentanyl arm

Abbreviations: RR=respiratory rate, OTFC=oral transmucosal fentanyl citrate, SC=subcutaneous

The role of rapid onset opioids. The episodic and transient nature of breakthrough dyspnea makes fast onset opioids an attractive option. Administration of opioids intravenously or subcutaneously can allow rapid delivery of the drug, although many patients do not have access to these routes at home. Fentanyl is a highly lipophilic compound. Over the past decade, there has been active development of fentanyl, including delivery by the transmucosal (oral transmucosal fentanyl citrate [OTFC], Actiq), buccal (Fentora), intranasal (Lazanda, Instanyl) and sublingual (Subsys, Abstral) formulations ¹⁸⁻²⁰. These fentanyl formulations have been successfully used to manage breakthrough pain ²¹⁻²⁸, although their role in breakthrough dyspnea has only been reported in a handful of studies. Two small retrospective case series reported on the use of transmucosal and intranasal fentanyl ^{15,16} and one prospective series examined the use of OTFC ¹⁷ suggest significant improvement in breakthrough dyspnea with these agents. Randomized controlled trials are urgently needed to confirm these findings with rapid onset opioids, which could potentially open up a new therapeutic indication for these medications.

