This contribution will be significant because it represents a key step in a continuum of research that is expected to lead to the optimization of FSS to relieve exertional dyspnea in cancer patients and to improve their function and quality of life. If the preliminary results from this randomized trial demonstrate a significant effect with FSS, the next step will be to conduct a larger, multi-institutional randomized controlled trial that is adequately powered. Further confirmation of FSS's efficacy would pave the way for using this medication for a novel indication. The proposed study has the potential to greatly improve patients' symptom burden, function and quality of life, and shift the paradigm for symptom research.

C. Experimental Approach

C.1. Overall Study design. This is an investigator-initiated study supported by Insys Therapeutics Ltd. We propose a 2-arm, double-blind, parallel randomized controlled trial of FSS for cancer patients with breakthrough dyspnea (Figure 1). The main goal of this study is to determine the effect size of FSS on dyspnea (at two different doses) to inform a larger, adequately powered confirmatory randomized controlled trial. After study consent, eligible patients will be asked to complete a number of surveys and a shuttle walk test at baseline, rest until they return to baseline dyspnea, and then do another shuttle walk test after they have been given FSS prophylactically.

Based on our experience conducting symptom control trials, this study will take each patient approximately 2 hours to complete in a single visit. We believe this study design is feasible and would not add undue burden for patients. Patients will be compensated with a \$50 gift card and a \$15 parking voucher for their time and effort after they have completed the study assessments.

C.2. Eligibility Criteria. The eligibility criteria are shown in Table 2.

Figure 1. Study Flow Chart

Table 2. Study Eligibility Criteria

Inclusion Criteria
1. Diagnosis of cancer with evidence of active disease
2. Breakthrough dyspnea, defined as dyspnea with an average intensity level over the past 7 days of at least 3/10 on a numeric rating scale upon significant exertion or continuous dyspnea </=7/10 with worsening upon significant exertion
3. Outpatient at MD Anderson Cancer Center seen by the Supportive Care Service, Thoracic Medical Oncology, Cancer Pain Clinic, or Cardiopulmonary clinic
4. Ambulatory and able to walk with or without walking aid

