not take the study medication is as follows: In CTC, edit the patient to be replaced modifying MRN within the specific patient's stratum. Then add a history of the changes made to the Notes section. Randomization will be 1:1 between the two study arms with permuted blocks, and stratified by baseline level of dyspnea modified Borg scale at rest at the time of enrollment (i.e. 0-3, 4-6).

C.5. Blinding. Both the patient and the research staff conducting the assessment will be blinded to the treatment assignment. FSS will be dispensed by Dispensing Pharmacy at MD Anderson. Only research nurse administering the medication will be aware of the study dose, and will be instructed not to share that information with the patient and other research staff. Further to that, we will check the blinding from patients and study staff at the end of study.

C.6. Research staff. An orientation will be held with research staff involved in this study to introduce them with the study design and to standardize the provision of each intervention.

C.7. Study Interventions. The commercial supply of study medication will be provided by Insys Therapeutics Ltd. We will use a one time prophylactic FSS dose equivalent to either 15-25% or 35-45% of MEDD 10 minutes prior to the second shuttle walk test. FSS was FDA approved in 2012 for "For the management of breakthrough pain in adult cancer patients who are already receiving and who are tolerant to around-the-clock opioid therapy for their underlying persistent cancer pain."

Immediately upon patient enrollment, the study physician will be notified and will determine the morphine equivalent daily dose (MEDD) in real time using standardized equianalgesic ratios. Based on clinical practice and similarly to the dose used for breakthrough pain, we will use an FSS dose equivalent to 15-25% or 35-45% of MEDD (Table 3). The study medication will be provided by Dispensing Pharmacy and will then be administered 10 minutes before the second shuttle walk test. We estimated the FSS dose based on the following assumptions:

- A one time rescue dose 15-45% of the MEDD is safe and effective for relief of dyspnea
- FSS has approximately 70% oral bioavailability ³⁰

Table 3. Proportional Dosing of FSS for patients randomized to the two study arms

High dose (target 35-45% MEDD)				Low dose (target 15-25% MEDD)			
MEDD (mg/day)	FSS dose*	% of MEDD - low	% of MEDD - high	MEDD (mg/day)	FSS dose*	% of MEDD - low	% of MEDD - high

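### FSS always coincides with the second walk, so the change between walks cannot show an advantage of FSS over no FSS

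*Combined protocol and SAP*

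**What the plan says.** The primary objective in Section A is to determine what prophylactic FSS does to exertional dyspnea from the first shuttle walk (Walk 1) to the second (Walk 2), and it continues: "We aim to estimate the effect size for both FSS arms to inform a larger, adequately powered confirmatory randomized controlled trial". A.2 applies the same comparison to walk distance and adverse effects and states: "We hypothesize that FSS is superior to no FSS in increasing walk distance and has limited side effects in opioid tolerant individuals". A.3 is a different comparison, high against low dose, with the hypothesis that the higher dose does better in "reducing dyspnea at the end of the shuttle walk test".

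The design is in Section C. Under C.1, patients complete Walk 1, rest, and then "do another shuttle walk test after they have been given FSS prophylactically". C.7 gives a single FSS dose 10 minutes before Walk 2 in either arm, and the arms differ only in the proportional dose. On allocation, C.4 says: "Randomization will be 1:1 between the two study arms with permuted blocks". C.5 and footnote 12 of Table 5 blind and check the dose level only; a patient's guess can be high, low or unknown. C.9 says Walk 1 is there to let each patient serve as their own comparator.

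D.1 plans 15 evaluable patients per arm. It says the study is not powered to compare arms, and gives 80% power for a standardised effect of 0.778 with a two-sided paired t-test at 0.05. D.2 plans descriptive summaries with 95% confidence intervals and an optional repeated-measures model that would also estimate a treatment effect.

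**The concern.** No patient does a second walk without FSS, and no patient does a first walk with it. The only observation without FSS is the earlier walk in the same person. Whatever else differs between a first and a second walk on the same visit is therefore part of the quantity that Section A attributes to the drug. That includes familiarity with the test, knowing that active drug has just been given, and incomplete recovery or accumulated fatigue. Practice and expectation would tend to flatter FSS and fatigue would tend to hide it, so the net direction is unknown.

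Two readings of the results are at stake. An improvement within an arm could be reported as FSS beating no FSS, and a flat result could be reported as FSS doing nothing. Neither follows. The study's stated product is an effect size for a later trial, so it matters that this number is labelled for what it measures.

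**Working it through.** **Step 1: what the design identifies.** From C.1, C.4 and C.7 there are four arm-by-walk means.

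| Cell | Intercept | High arm | Walk 2 | FSS given | High × FSS |
|---|---|---|---|---|---|
| Low dose, Walk 1 | 1 | 0 | 0 | 0 | 0 |
| Low dose, Walk 2 | 1 | 0 | 1 | 1 | 0 |
| High dose, Walk 1 | 1 | 1 | 0 | 0 | 0 |
| High dose, Walk 2 | 1 | 1 | 1 | 1 | 1 |

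The Walk 2 and FSS columns are identical, so the matrix has rank 4 for 5 parameters. Two things about the change can be estimated:
- the sum (Walk 2 effect + FSS effect), which is the low-arm change;
- High × FSS = (high-arm change) − (low-arm change), which is the randomised dose contrast.

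More time points, or a term for distance walked, do not help. They add no observation in which the two columns differ. The treatment effect in D.2's model can therefore mean only high versus low dose.

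**Step 2: reproduce D.1.** Inputs from D.1: n = 15, d = 0.778, two-sided 0.05, paired t-test. Noncentrality = d × √n = 0.778 × √15 = 3.013, with 14 degrees of freedom. Power from the noncentral t = 0.79998, or 80.0%. D.1's figure is correct for the test it names.

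**Step 3: what that power refers to.** The test sees only the total standardised change, d = d(FSS) + d(non-drug). Set d(FSS) = 0 and assume values for d(non-drug), in SD units of the change, because the documents give none.

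| Assumed non-drug shift (SD) | Noncentrality | Probability that one arm is significant |
|---|---|---|
| 0 | 0 | 5.0% |
| 0.2 | 0.775 | 11.2% |
| 0.3 | 1.162 | 19.2% |
| 0.4 | 1.549 | 30.3% |
| 0.5 | 1.936 | 43.8% |
| 0.778 | 3.013 | 80.0% |

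The last row shows that D.1's 80% is power to detect any change from Walk 1 to Walk 2 of that size, whatever its source.

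The opposite case follows from the same table. If FSS truly gave 0.778 SD and fatigue took away an assumed 0.278 SD, the net shift would be 0.778 − 0.278 = 0.5 SD. The probability of a significant result would fall from 80% to 44%.

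**Step 4: what 15 per arm can say about the identified contrast.** Assume a common SD of the change in the two arms. The 95% confidence interval half-width for high minus low is t(0.975, 28) × √(2/15) = 2.048 × 0.365 = 0.748 SD. A two-sample test at this size has 80% power only for a difference of 1.06 SD.

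**The case against.** The strongest defence is that this is a pilot that does not pretend otherwise. D.1 presents the aim as learning the distribution of dyspnea scores in each arm. The primary objective and D.1 both say openly that the comparison is between the two walks. The superiority sentence in A.2 is a hypothesis about distance with no test attached, and the paired t-test appears only in the power statement while D.2 is mainly descriptive. A later controlled trial would correct a false lead.

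There are also real safeguards. The walk is externally paced, the explanation is standardised, the operator walks alongside for the first minute, and the test is cited as reproducible (C.9, including the procedure text around Table 4). Patients rest before dosing under a recovery rule (C.10) and are advised to avoid breakthrough opioids and bronchodilators (C.8).

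Much of this stands. The safeguards may well keep practice and carry-over small, and the within-arm changes are legitimate descriptive results. But pilot status affects precision, not what a number measures. None of the safeguards supplies a second walk without FSS, and none addresses the expectation that comes with knowing active drug was given. Describing the comparison as between walks does not help while the same sentences call it an FSS effect.

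It also stands that the A.3 contrast is sound. Both arms share the same order, practice and expectation of active drug, so a dose difference would be controlled, though imprecise, evidence of a drug effect. It is still not a comparison with no FSS.

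**Conclusion.** The concern holds as a matter of design and labelling. The change from Walk 1 to Walk 2 within an arm estimates FSS plus second walk, and it cannot support the A.2 hypothesis. The identification result rests on the design alone. The 11% to 44% figures rest on assumed shifts of 0.2 to 0.5 SD and on an approximately normal change score; they illustrate sensitivity and do not predict bias.

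Four stronger readings are tempting, and the documents do not support them:

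- A reader might take the controlled trial in Table 1, with falls of 1.0, 0.9 and 0.8 across arms that include nebulised saline, as sizing the non-drug shift here. The Background says it "found no significant difference in dyspnea relief at 10 minutes between the treatment arms", so it does show that dyspnea can fall without active opioid. But no scale is given, and an existing episode was subsiding there, whereas here dyspnea is induced again after rest.
- A reader might treat the Significance text, "If the preliminary results from this randomized trial demonstrate a significant effect with FSS, the next step will be to conduct a larger", as a go/no-go rule met by the paired t-test. It is narrative, it does not define significance, and it is not tied to D.1.
- A reader might infer a bias of known size from the rest rule's one-point allowance in C.10. That check precedes dosing and a further 10-minute wait, so residual dyspnea at the start of Walk 2 is not established.
- A reader might infer material selection from the C.11 rule on patients with no rise in dyspnea at Walk 1. The protocol calls that situation unexpected and gives no rate.

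**What to change.** 1. In the primary objective and A.2, describe the estimand as the within-patient change from Walk 1 to Walk 2 after FSS, in each dose arm, and delete the claim of superiority to no FSS.
2. In D.1 and D.2, state that this change includes non-drug effects of unknown direction and will not be interpreted as FSS against no FSS. State also that the treatment effect in the D.2 model means high versus low dose.
3. In D.2, commit to reporting what the next trial can use from this design: the SD of the change, the correlation between Walk 1 and Walk 2, and the high-minus-low difference with its 95% confidence interval (about ±0.75 SD at 15 per arm).

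The cost is a more modest claim: the stated aim becomes an estimate of change and of a dose difference, and any FSS-versus-control difference for a later trial has to come from elsewhere. Arms, sample size and procedures are unchanged.

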Fentanyl sublingual spray (FSS) is a particularly attractive option for breakthrough dyspnea. It was approved by the US Food and Drugs Administration in 2012 for “the management of breakthrough pain in adult cancer patients who are already receiving and who are tolerant to around-the-clock opioid therapy for their underlying persistent cancer pain”, and represents an alternative delivery system for fentanyl that also utilizes a transmucosal route like OTFC. A pharmacokinetic study examining 5 different doses of FSS (100 mcg, 200 mcg, 400 mcg, 600 mcg, 800 mcg) in healthy volunteers demonstrated that fentanyl enters the systemic circulation rapidly, achieving 27%, 61%, 87% and close to 100% of maximal plasma concentration (Cmax) within 5, 10, 20 and 30 minutes, respectively ²⁹. In a separate crossover study comparing FSS 400 mcg, OTFC 400 mcg and intravenous fentanyl 100 mcg in healthy volunteers, FSS had a greater bioavailability (76% vs. 51%) and achieved a higher Cmax than OTFC (0.81 mg/ml vs. 0.61 ng/ml). Similar to the previous study, the mean plasma concentrations were 19% and 54% of Cmax within 5 and 10 minutes ³⁰. In a double-blind, randomized placebo controlled trial, FSS provided greater and more rapid pain relief, and significantly reduces pain compared to placebo at 5, 30 and 60 minutes ²⁸. The most common adverse effects included nausea (7%), hyperhidrosis (5%) and peripheral edema (5%).

Significance. We expect to advance the understanding of how FSS can be used to treat exertional dyspnea in cancer patients. The effective management of dyspnea may ultimately help alleviate this devastating symptom. A better fundamental understanding of how this intervention improves physiologic parameters could also shed light on the pathophysiologic characteristics of dyspnea and allow us to devise new and more effective treatments.

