5. On strong opioids with morphine equivalent daily dose of 80-500 mg for at least one week, with stable (i.e. +/- 30%) regular dose over the last 24 hours
6. Karnofsky performance status >/=50%
7. Age 18 or older
8. Able to complete study assessments
Exclusion Criteria
1. Dyspnea at rest >/=7/10 at the time of enrollment
2. Supplemental oxygen requirement >6 L per minute
3. Delirium (i.e. Memorial delirium rating scale >13)
4. History of unstable angina or myocardial infarction 1 month prior to study enrollment
5. Resting heart rate >120 at the time of study enrollment
6. Systolic pressure >180 mmHg or diastolic pressure >100 mmHg at the time of study enrollment
7. History of active opioid abuse within the past 12 months
8. History of allergy to fentanyl
9. Severe anemia (Hb <7g/L) if documented in the last month and not corrected prior to study enrollment*
10. Diagnosis of acute pulmonary embolism within past 2 weeks
11. Diagnosis of pulmonary hypertension
12. Unwilling to provide informed consent

* To minimize study burden for participation in this 2-hour study, extra bloodwork will not be drawn unless the patient already has the above lab abnormalities documented and need to be corrected.

C.3. Study screening. A 2 step consent process will be used. First, a verbal consent will be obtained by the study staff to proceed with screening of potential participants for eligibility and to characterize their dyspnea using the dyspnea survey and the cancer dyspnea scale. Outpatients may be contacted by phone within 1 week prior to their scheduled clinic visit to inform them of this study so they can make necessary arrangements if interested in participating. Eligible patients will then be formally enrolled onto the study after they have signed the informed consent indicating a willingness to participate in the trial. The number of patients screened, approached, eligible, and enrolled will be documented. Reasons for refusal for eligible patients will also be captured.

C.4. Randomization. Patient randomization will be conducted through the Clinical Trial Conduct (CTC) website (<https://biostatistics.mdanderson.org/ClinicalTrialConduct>), which is maintained by the Department of Biostatistics at MD Anderson Cancer Center. The trial statistician will train the users (pharmacists or research nurses) in the use of this website for randomizing patients. The methodology to replace a patient who does

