80-100	200	35.0	43.2	80-130	100	13.5	21.6
101-150	300	35.0	52.0	131-210	200	16.7	26.7
151-200	400	35.0	46.4	211-280	300	18.8	24.9
201-250	500	35.0	43.5	281-450	400	15.6	24.9
251-300	600	35.0	41.8	451-500	600	21.0	23.3
301-400	800	35.0	46.5				

401-500 1000 35.0 43.6 |

* FSS comes in 100 mcg, 200 mcg, 400 mcg, 600 mcg and 800 mcg. A combination of these products would allow us to deliver the desired dose.

The following instructions will be given to the patient:

1. Swallow any saliva in your mouth.
2. Hold the medication spray unit upright using your index and middle fingers and thumb.
3. Point the nozzle into your mouth and under your tongue.
4. Squeeze your fingers and thumb together to spray the medication under your tongue.
5. Hold the medicine under your tongue for 30-60 seconds. Do not spit out any medicine. Do not rinse your mouth.
6. The spray unit will remain locked after use.

C.8. Medication use during study. To minimize the co-intervention effect on dyspnea, patients will be advised to avoid using breakthrough opioids (for any reason) or bronchodilators for at least 2 hours prior to and during the study.

C.9. The Shuttle walk test is an externally paced test, and has been found to be high reproducible for inducing breathlessness in patients with advanced cancer ³¹⁻³³. Furthermore, the shuttle walk test was reported to be equivalent or better than 6 minute walk test in detecting a clinical response ³⁴⁻³⁶. Shuttle walk tests will be conducted according to published procedures ³¹⁻³³. The first shuttle walk test is designed to provide important information regarding a patient's level of dyspnea on exertion, and to facilitate intra-individual comparison since there is significant variability in the expression of dyspnea among patients. The second shuttle walk test will be conducted 10 minutes after study medication has been administered.

The research staff conducting the walk test must be certified in cardiopulmonary resuscitation with a minimum of Basic Life Support by an American Health Association-approved cardiopulmonary resuscitation course. Walking aid is allowed as long as patients keep them the same as before enrollment and during the entire study.

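### Table 3 assigns doses outside the arm definitions (15-25% and 35-45% of MEDD) and outside the 15-45% range that section C.7 assumes to be safe and effective

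*Combined protocol and SAP*

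**What the plan says.** The primary objective in section A names the two arms by dose: "FSS, 15-25% and 35-45% proportional doses". Section C.7 gives the same ranges twice, the second time pointing to the dosing table: "we will use an FSS dose equivalent to 15-25% or 35-45% of MEDD (Table 3"). C.7 then lists the assumptions behind the doses. The first is "A one time rescue dose 15-45% of the MEDD is safe and effective for relief of dyspnea". The second is a bioavailability of about 70%, citing reference 30.

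Table 3 gives one dose in mcg for each MEDD band and prints the lowest and highest percentage of MEDD that the dose represents. Its headings use the word target, as in "High dose (target 35-45% MEDD"). One high-arm row reads "101-150 300 35.0 52.0", that is, 300 mcg for MEDD 101-150, giving 35.0% to 52.0%. The footnote lists the product strengths and adds: "A combination of these products would allow us to deliver the desired dose". Inclusion criterion 5 in Table 2 admits patients on a "morphine equivalent daily dose of 80-500 mg", so every band of the table can be used.

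Section B, also citing reference 30, reports that "FSS had a greater bioavailability (76% vs. 51"%), the comparator being oral transmucosal fentanyl.

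**The concern.** The text treats Table 3 as delivering the stated ranges, but the table's printed columns leave them in both arms. Three of the seven high-arm bands exceed 45% at their upper end (52.0%, 46.4%, 46.5%). In the low arm, one band falls to 13.5% and another reaches 26.7%. Four of these five values also lie outside the 15-45% premise; 26.7% breaks only the arm range. For the affected MEDD values, a dose cannot agree with both the arm definition and the table.

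The study exists to supply effect sizes and adverse-effect data at two named doses for planning a larger trial. As written, those results would carry labels that do not describe every dose assigned, and the stated safety assumption would not cover some of the opioid doses in the table.

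**Working it through.** **Inputs.** Arm ranges of 15-25% and 35-45% (sections A and C.7); assumed safe and effective range of 15-45% (C.7); bands, doses and 24 printed percentages (Table 3); eligible MEDD of 80-500 mg/day (Table 2). The conversion factor is not printed, so it has to be back-solved.

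**Reproducing Table 3.** Percentage of MEDD = 100 × k × dose (mcg) / MEDD (mg). Setting 200 mcg at MEDD 100 to 35.0% gives k = 0.35 × 100 / 200 = 0.175 mg per mcg, which equals 0.25 × 0.70. This single factor reproduces 22 of the 24 printed percentages to one decimal, so the out-of-range values are the table's own arithmetic and not a reading error in the PDF. The five that matter are:

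| Arm | MEDD | Dose (mcg) | Calculation | Printed |
|---|---|---|---|---|
| High | 101 | 300 | 52.5/101 = 51.98% | 52.0 |
| High | 151 | 400 | 70/151 = 46.36% | 46.4 |
| High | 301 | 800 | 140/301 = 46.51% | 46.5 |
| Low | 130 | 100 | 17.5/130 = 13.46% | 13.5 |
| Low | 131 | 200 | 35/131 = 26.72% | 26.7 |

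The two cells that do not reproduce are 43.2 and 21.6, the upper values of the first band in each arm. At MEDD 80 the factor gives 35/80 = 43.75% and 17.5/80 = 21.9%; the printed figures match MEDD 81. Both cells stay in range at 80.

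**How much of the MEDD range is affected.** Applying the table to each whole-mg MEDD from 80 to 500 (421 values):

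- High arm above 45%: 101-116, 151-155 and 301-311, so 16 + 5 + 11 = 32 values (32/421 = 7.6%).
- Low arm below 15%: 117-130, 14 values. Low arm above 25%: 131-139, 9 values. Together 23 (23/421 = 5.5%).
- Outside the 15-45% assumption: 32 + 14 = 46 of the 55 out-of-range values.

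**Do the product strengths force it?** The listed strengths combine only to multiples of 100 mcg, or 17.5 mg morphine equivalent per unit. A whole number n with 17.5n/MEDD inside the arm's range was sought at each of the 55 values. None exists at 21 high-arm values (101-116, 151-155) or at any of the 23 low-arm values (117-139): 44 in all. At MEDD 110, for example, 35/110 = 31.8% and 52.5/110 = 47.7%, on either side of 35-45%. At the other 11 (high arm, 301-311) a multiple does fall in range.

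**Separation of the arms.** The highest low-arm value is 26.7% and the lowest high-arm value is 35.0%. At equal MEDD the high:low dose ratio runs from 300/200 = 1.5 to 300/100 = 3.0, inside the 35/25 = 1.4 to 45/15 = 3.0 that the nominal ranges allow.

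**Patients, under assumed MEDD distributions only.** With 15 per arm and MEDD spread evenly over 80-500: 15 × 32/421 = 1.1 in the high arm and 15 × 23/421 = 0.8 in the low arm. With MEDD skewed low (lognormal, median 120, log-SD 0.5, cut to 80-500): about 2.7 in each arm. Neither distribution comes from the documents.

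**Bioavailability, sensitivity only.** If the conversion scaled in proportion to bioavailability, 76/70 = 1.086 would turn 35.0-52.0% into 38.0-56.4% and 13.5-26.7% into 14.6-29.0%. That scaling is an assumption, because the conversion is not shown.

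**The case against.** The strongest reply is that the departure is disclosed and mostly unavoidable. The table headings call the ranges targets, every band shows its true lowest and highest percentage, C.7 describes the doses as estimated, and at 44 of the 55 values no combination of available units meets the range. Staff have one lookup table with one dose per arm at every MEDD, so in practice they would follow it. Most excesses are small: the 32 high-arm values average about 2.1 points above 45%, only the 101-150 band exceeds 47%, and MEDD 117 and 311 sit at the limit once rounded to the table's one decimal. The arms remain distinct, sections D.1 and D.2 do not use the percentage as a variable, and the input is itself loose, since eligibility accepts a regular dose stable only to within 30%.

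Much of this stands, and it limits the weight of the point: the comparison between arms is not damaged, and the number of patients affected is unknown. It does not remove the conflict. No tolerance is stated anywhere; the objectives and C.7 give the ranges without calling them targets; and the 15-45% premise is not a target at all, yet the table exceeds it by up to seven points. If rounding to unit strengths is the reason, the protocol should say so, whereas the footnote says that combining products achieves the intended dose. Unit strength also does not explain the 11 values at 301-311.

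The bioavailability difference is a loose approximation that calls only for confirmation, and the two mismatched cells are minor. Neither carries the conclusion.

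**Conclusion.** The concern holds, and the conflict must be resolved before dosing because it concerns a single opioid dose that the protocol's own safety premise does not fully cover. The printed spans, 13.5-26.7% and 35.0-52.0%, contradict the arm definitions in both arms and contradict the 15-45% assumption at both ends. That conclusion rests on the printed columns alone. The counts of affected MEDD values also need the back-solved factor of 0.175 mg per mcg, which is well supported by the 22 matching cells. Changing the band edges alone cannot cure the problem, because 44 of the 55 affected values have no dose in range at the listed strengths. How many of the 30 patients would be affected cannot be known from the documents.

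**What to change.** - Before dosing, the investigators should reconcile Table 3, the arm definitions in sections A and C.7, and the 15-45% assumption, and state any tolerance they intend. Which of these is right is for them to decide.
- Confirm which bioavailability figure underlies the conversion (about 70% in C.7, 76% in section B, same reference) and show the conversion.
- Make the dose description in the objectives and in reports match what the reconciled table delivers.
- Reconcile the 43.2 and 21.6 cells with the band edge and eligible minimum of 80; as printed they correspond to 81.
- In section D.2, add a summary by arm of each patient's actual dose as a percentage of MEDD. Keep it descriptive: within an arm, the percentage is fixed by baseline MEDD, so relating it to outcome would confound dose with opioid requirement.

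The cost is protocol wording, a corrected table and one variable derived from data already collected, with no extra patients or visits. The drawback is a less tidy description of dose.
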